7.2.4 Summary of Analyses

The list below is not an exhaustive list of statistical analyses that will be performed for objective 1.

Outcome	Analysis Set	Supports Protocol Objective Number	Subgroup	Statistical Method	Covariates/Strata	Missing Data
External Control dataset	Full analysis set	1	None	Propensity score matching or IPW via Logistic regression	Demographic and clinical characteristics, including baseline comorbidities.	Excluded
Height Z-Score (and other Anthropometric endpoints)	Full analysis set	2	None	Mixed model repeated measures model, Propensity Score Matched or IPW	Propensity Score Matched, or data augmented by IPW, by Demographic and clinical characteristics.	Excluded

10 APPENDICES

10.1 APPENDIX 1: DATA DERIVATION DETAILS

A1.1 Definition and use of visit windows in reporting

Visit Label	Target Day	Start Day	End Day
Screening	NA	Day -14	Day -1
Day 1	Day 1	Day 1	Day 1
Day 4	Day 4	Day 2	Day 6
Day 8	Day 8	Day 7	Day 9
Day 15	Day 15	Day 10	Day 19
Day 29	Day 29	Day 20	Day 39
Month 2	Day 61	Day 40	Day 75
Month 3	Day 91	Day 76	Day 105
Month 4	Day 121	Day 106	Day 135
Month 5	Day 151	Day 136	Day 165
Month 6	Day 181	Day 166	Day 195
Month 7	Day 211	Day 196	Day 225
Month 8	Day 241	Day 226	Day 255
Month 9	Day 271	Day 256	Day 285
Month 10	Day 301	Day 286	Day 315
Month 11	Day 331	Day 316	Day 345
Month 12	Day 365	Day 346	Day 366

A1.2 Further definition of endpoints

Height Z-score, as well as standing height and arm-span were measured in triplicate. For each subject the result at a given visit is an average of the triplicate results.

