2.1 STUDY DESIGN

• This is a retrospective cohort study using existing data from two ongoing studies: C4181001 and C4181005. The study population will include two independent study

PFIZER CONFIDENTIAL

CT24-WI-GL03-RF03 2.0 Non-Interventional Statistical Analysis Plan For Secondary Data Collection Study 01-Jun-2020 Page 5 of 17 cohorts: a) patients from Study C4181005 who have completed Visits 1 through 11 (at D183); b) patients from Study C4181001 who meet the eligibility criteria for Study C4181005 and have at least 6 months follow-up data. Eligible patients from Study C4181001 will be included as potential external controls for patients in Study C4181005, using propensity score methodology.

This pilot study has the potential to demonstrate the feasibility of Study C4181001 as concurrent external controls and provide viable study design options for the recifercept pivotal trial. It will also provide information on the efficacy of recifercept compared to clinical practices in the real world. Having an external control arm in the trial allows for increased efficiency and decreased product development time.

Study population

This retrospective cohort study will include achondroplasia patients from Study C4181005 and those from Study C4181001 who meet the inclusion and exclusion criteria of Study C4181005. Study C4181005 is a single-arm trial to evaluate the safety and tolerability of recifercept doses and dosing regimen, and efficacy to increase height growth in achondroplasia patients. Study C4181005 will include approximately 63 children with achondroplasia aged 3 months to 10 years (inclusive) with Tanner Stage 1. who are enrolled and randomized to receive one of three doses of recifercept (1mg/kg once-weekly, 2mg/kg twice-weekly, or 1.5mg/kg once-daily) subcutaneously for 12 months. Demographics, medical history, anthropometric measurements, and patientreported outcomes in functional status and quality of life are collected approximately every 3 months. Study C4181001 is a prospective natural history study to collect the longitudinal anthropometric and disease-related complication data in children with achondroplais. It will include approximately 300 achondroplasia patients aged 0-15 years with Tanner Stage I recruited from global sites. Patient data will be collected at baseline and at every 3-month interval visits, for a maximum of 5 years. Further details on data sources are presented in Table 1.

Data source

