7.2 STATISTICAL ANALYSES

To evaluate objective 2, mixed-effect, repeated measures (MMRM) models will be used. The fixed effects of treatment, visit, treatment-by-visit interaction, age and gender will be included. Visit will be modeled as a categorical covariate. (If the model does not converge then Visit will be modeled as a continuous covariate.) There will be random effects for both slopes (i.e. visit as a continuous variable) and intercept, clustered by subject nested within a propensity-score matched set or clustered by subject weighted by Inverse Probability Weights (see section 10.3). Random effects for slopes will be removed in the above models do not converge. Unstructured covariance matrix will be assumed for the model errors.

7.2.1 Objective 1

To construct a concurrent external control for Study C4181005, a propensity score (PS) will be created to achieve balance across covariates between achondroplasia patients from Study C4181005 and patients from Study C4181001 who meet all the eligibility criteria of Study C4181005. The PS will be estimated using standard logistic regression approaches with the "outcome" variable being the data source (whether patients were included in Study C4181005 and exposure to recifercept treatment) and the predictors being the variables associated with both the exposure (recifercept treatment) and the outcomes of interest (i.e. standing height & arm-span-to-height difference). This model will provide the predicted probability of being in the trial cohort relative to the concurrent external control cohort as a function of the covariates (the propensity score of being included in Study C4181005). The potential covariates may include demographics (e.g. age, gender, race and ethnicity), clinical characteristics (e.g. presence of achondraplasia-related complications, Tanner stage, and other non-achondroplasia-

PFIZER CONFIDENTIAL

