Another method to construct an external control for C4181005 for the purpose of estimating the Average Treatment Effect (ATE) of recifercept is Inverse Probability Weights (IPW). IPW will use PS to weight the observations prior to the analysis of height growth. Weights are calculated for each subject as 1/PS for Recifercept and 1/(1-PS) for the untreated group. Standardized differences between the untreated and Recifercept groups will be assessed both before and after weighting. Standardized mean differences of <10% may be considered a negligible difference.

7.2.2 Objective 2

Achondroplasia disease measures including height growth, anthropometric measurements, difference in functional status and health-related of life will be summarized using descriptive statistics.

Analyses of Height Z-Score and Arm-Span-to-Height Difference

If objective 1 is met, either a matched dataset – exclusively with a ratio of treated to untreated of 1:1 - via PS or a dataset augmented by IPW will be used to analyze height Z-Score. Baseline summaries of Height Z-score and Arm-Span to Height-difference and change from baseline a months 3, 6, 9, and 12 will be presented.

7.2.3 Safety Analyses

Not applicable.

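### The SAP's only visit-window table is monthly, so a quarterly height 15 or more days late or 16 or more days early is labelled an in-between month and misses the planned summaries

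*SAP*

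**What the plan says.** SAP A1.1 has rows for screening, Days 1, 4, 8, 15 and 29, and then every month to Month 12. The rows that matter here are "Month 3 Day 91 Day 76 Day 105", "Month 4 Day 121 Day 106 Day 135", "Month 6 Day 181 Day 166 Day 195", "Month 9 Day 271 Day 256 Day 285" and "Month 12 Day 365 Day 346 Day 366". No study is named, controls have no row or rule of their own, and nothing maps an in-between label back to the nearest quarterly visit. The protocol has no window table.

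For the natural history study, SAP 2.1 says: "Patient data will be collected at baseline and at every 3-month interval visits, for a maximum of 5 years". SAP Table 1 puts anthropometry at every 3 months in both studies. Protocol Table 3 (section 9.3) adds a 1-month measurement in the trial only.

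For reporting, SAP 7.2.2 says that "change from baseline a months 3, 6, 9, and 12 will be presented". SAP section 6 rules out imputation. For the model, SAP 7.2 says "Visit will be modeled as a categorical covariate", adds a treatment-by-visit interaction, and allows continuous visit only if the model does not converge. The code in SAP 10.3 leaves month out of the CLASS statement in both models, so there it is continuous from the start.

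**The concern.** The windows are set for a monthly grid, but the endpoints are measured quarterly. On such a grid, a 3-month height taken on Day 110 is labelled Month 4 and a 6-month height taken on Day 160 is labelled Month 5. Both are valid measurements made for a planned visit, yet neither label is among the months to be reported.

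Two things are at stake. The by-month summaries can lose valid heights, and what remains is selected on how punctual the visit was. In the model that the SAP text describes, each stray label becomes its own visit level with its own treatment interaction, estimated from few children. The project is meant to show whether the natural history study can serve as a control arm, so lining up visits across the two studies is a basic step.

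**Working it through.** **Inputs.** Target, start and end days are from SAP A1.1. The quarterly schedule is from SAP 2.1 and Table 1, and the reporting months are from SAP 7.2.2. The spread of actual visit days is not in the documents and is assumed below.

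**1. Reproduce the windows.** Each interior window runs from the midpoint with the previous monthly target to the day before the midpoint with the next.
- Month 3: (61 + 91)/2 = 76; (91 + 121)/2 − 1 = 105.
- Month 6: (151 + 181)/2 = 166; (181 + 211)/2 − 1 = 195.
- Month 9: (241 + 271)/2 = 256; (271 + 301)/2 − 1 = 285.

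All three match the table exactly.

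**2. Tolerance around target.** 76 − 91 = −15 and 105 − 91 = +14. Targets 181 and 271 give the same. The Month 12 row gives 346 − 365 = −19 and 366 − 365 = +1.

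**3. Labels off target.** A height 15 days late becomes Month 4, 7 or 10. A height 16 days early becomes Month 2, 5 or 8. A 12-month height 20 days early (Day 345) becomes Month 11. The windows have no gaps from Day 1 to Day 366, so every height in that range keeps some label.

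**4. Share outside the Month 3, 6 or 9 window.** Assume that the actual day is normal around target, recorded in whole days:

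share = P(Z < −15.5/SD) + P(Z > 14.5/SD)

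For quarter-centred windows of −45/+44 days:

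share = P(Z < −45.5/SD) + P(Z > 44.5/SD)

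| SD of visit day | As written (−15/+14) | Quarter-centred (−45/+44) |
|---|---|---|
| 5 | 0.3% | 0.0% |
| 10 | 13.4% | 0.0% |
| 14 | 28.4% | 0.1% |
| 21 | 47.5% | 3.2% |

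With uniform timing the share as written is 0% if all visits fall within 14 days of target. Within 21 days it is 13 of 43 possible days, or 30.2%.

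**5. Quarter-centred edges.** Midpoints of targets 1, 91, 181, 271 and 365 are (1 + 91)/2 = 46, (91 + 181)/2 = 136, (181 + 271)/2 = 226 and (271 + 365)/2 = 318. Starting Month 12 at Day 316 instead of 318 keeps an edge already in the table and gives Month 9 the same −45/+44 tolerance (226 − 271 and 315 − 271).

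**The case against.** The strongest reply is that little is actually lost. A1.1 is contiguous to Day 366, the hypothesis in SAP 3.1 concerns change up to 12 months, and the appendix code treats month as continuous. A Day 110 height then enters as Month 4, which is closer to the truth than Month 3 (11 days from Day 121 against 19 from Day 91). This stands: the effect on the coded between-group test is smaller than on the by-month results. It does not rescue the summaries or the categorical model that the SAP text puts first.

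It can also be said that A1.1 does not state that it governs controls, that windowed labels replace scheduled ones, or how a control's study day is counted. That is so. Its application to controls is inferred from the absence of any other table. If another rule is intended, the SAP needs to state it.

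Wide windows have a cost as well. A height 44 days late would count as Month 3, and the arm-span-to-height difference is not described as age-standardised, so its change depends on elapsed time.

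Two stronger readings are tempting:
- **Controls lose far more heights than treated children.** Setting SD 14 for controls against SD 5 for the trial gives 28.4% against 0.3%, but the documents support neither figure. The same windows apply to both groups, so equal timing spread gives equal loss.
- **The stray levels will make the model fail to converge.** This has not been shown. The text already combines random slopes and intercepts with an unstructured error covariance, which may cause trouble whatever the windows.

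**Conclusion.** The point holds as a mismatch between the window table and the measurement schedule. A quarterly height 15 or more days late, or 16 or more days early, falls outside the Month 3, 6 and 9 summaries. Month 11 does the same to early 12-month heights. In the categorical-visit model these heights form thin extra levels. The trial's planned 1-month measurement adds another level, with no scheduled control counterpart.

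That the mismatch exists follows from the table, on the inference that it covers both groups. How many heights it affects depends on visit timing that the documents do not give: from 0.3% to 47.5% over SDs of 5 to 21 days, and none if every visit is within 14 days of target. The documents do not support a claim of deleted data, of bias between groups, or of certain model failure. The SAP should be corrected, because the remedy is cheap and the present rule works against the reporting schedule.

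**What to change.** For the anthropometric endpoints, in both groups, replace the monthly rows of A1.1 with:
- Month 3: Days 46-135.
- Month 6: Days 136-225.
- Month 9: Days 226-315.
- Month 12: from Day 316, absorbing Month 11, with its end day settled when the Month 12 window is reviewed.
- The 1-month (Day 29) window: extended to Day 45, so that Days 40-45 are not orphaned when Month 2 goes. Keep this treated-only visit out of the categorical visit-by-treatment comparison.

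Take the height closest to the target day when several fall in one window; A1.1 has no such rule now. State that the table covers controls and how their study day is counted. Use actual study day wherever visit is modelled as continuous, so that wider labels do not coarsen time in that model.

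The cost is a table edit and a relabelling step, with no new data. The distribution of visit days can be checked without looking at outcomes. The downside is more timing spread within each label, which the closest-to-target rule limits and the actual-day run checks.

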10.2 APPENDIX 2: ADDITIONAL STATISTICAL METHODOLOGY DETAILS

A2.1 Further Details of the Statistical Methods

10.3 APPENDIX 3: DIAGNOSIS AND PROCEDURE CODES USED IN THE STUDY

Propensity Score Matching

proc psmatch data = adsl ;

class SEX DRUG WHITE ;

psmodel DRUG (treated = 'Recifercept') = SEX AAGE WHITE ;

match method = varratio (kmax = 4) distance = lps exact = (SEX WHITE);

assess lps allcov / weight = none plots = (barchart boxplot);

```
output out(obs = match) = outasa lps = _Lps matchid = _MatchID ;
```

run;

PFIZER CONFIDENTIAL

CT24-WI-GL03-RF03 2.0 Non-Interventional Statistical Analysis Plan For Secondary Data Collection Study 01-Jun-2020 Page 16 of 17

MMRM with Propensity Score Matching clusters

```
proc mixed data = ps_match_mmrm ;
    by paramcd ;
    class _MatchID usubjid sex drug (ref = 'Not Treated') ;
    model chg = month drug / s ; /*** s = Solution for Fixed Effects ***/
    random int month / subject = usubjid(_MatchId) ;
run ;
```

Inverse Probability Weighting

```
proc psmatch data = adsl region = allobs ;
    class SEX DRUG WHITE ;
    psmodel DRUG (treated = 'Recifercept') = SEX AAGE WHITE ;
    assess lps var = (SEX AAGE WHITE) / weight = atewgt plots = (barchart boxplot) ;
    output out(obs = all) = ipw_ate ATEWGT = _ATE_ ;
```

run;

MMRM with Inverse Probability Weights

```
PROC GLIMMIX DATA = ate_ipw METHOD = quadrature (qpoints = 27) EMPIRICAL =
classical NOREML ;
NLOPTIONS GCONV = 1E-10 TECHNIQUE = TRUREG ;
where PARAMCD APSBLFL = "Y" ;
CLASS DRUG (REF = "Not Treated") USUBJID ;
MODEL CHG = DRUG MONTH / SOLUTION ;
RANDOM INT MONTH / subject = USUBJID WEIGHT = _ATE_ ;
```

RUN;

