3 HYPOTHESES AND DECISION RULES

3.1 STATISTICAL HYPOTHESES

This study includes an CCL element and specific hypotheses to be tested. That null hypothesis is limited to a comparison of height Z-Score. The null hypothesis for that objective is as follows:

Null: Mean Change from Baseline of Height Z-Score up to 12 months is no different between patients on treatment and patients in the natural history study.

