CT24-WI-GL03-RF03 2.0 Non-Interventional Statistical Analysis Plan For Secondary Data Collection Study 01-Jun-2020 Page 11 of 17 related conditions of medical significance). The distribution of the PS will be reviewed and patients with a PS in the areas of nonoverlap and/or with extreme PS values might be excluded to improve validity (PS trimming). Each patient in the PS trimmed receifercept group will be matched on a ratio of 1:1 with patients in the PS trimmed concurrent external control using optimal nearest neighbour matching with a maximum caliper of 1%. Pre- and post-matching balance will be assessed using standardized differences between these two PS-matched groups. A negative control outcome may also be identified to evaluate the pre- and post-matching balance. There are different options that will be considered while modelling via PS. These include:

- 1. Calipers: range from [.01,.25]
- 2. Statistic (used to match treated to control subject): logit of PS, minimizing difference of PS, Mahalanobis distance
- 3. Ratio match (treatment-to-untreated): 1-to-1, 1-to-m

Exact matching can be included within the PS model. Exact matching will be done by gender. A binary variable will be created to specify race. The variable will have the value of "Yes" for "White" and "No" for all other values.

Standardized mean differences of the matched variables are the main criteria used to determine whether objective 1 is met. An external control dataset is confirmed (i.e., objective 1 is met) when all of the standard mean differences for the matched variables are less than 0.1.

After the concurrent external control is constructed by PS matching, descriptive statistics will be tabulated on patient demographic and baseline clinical characteristics between achondroplasia patients from PS-matched recifercept phase 2 trial cohort and those from PS-matched concurrent external control. Two-sample T-tests will be used for continuous variables, and chi-square tests for categorical variables assuming the distribution is normal. Frequency of primary, secondary and exploretary outcomes of interest and 95% confidence intervals will be computed.

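### The coded propensity score and balance check use only sex, age and White, so Objective 1 can be met while the groups differ at baseline on height Z-score, the tested endpoint

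*SAP*

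**What the plan says.** SAP 10.3 holds one matching program and one weighting program. Both specify the score as "psmodel DRUG (treated = 'Recifercept') = SEX AAGE WHITE", and both ASSESS statements cover only the logit score and those three variables. The code is not a mere example: SAP 7.2 refers to 10.3 for the models, and the SAP's list of amendments records that the code was added for the statistical analysis.

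SAP 7.2.4 gives the covariates for the external control dataset as "Demographic and clinical characteristics, including baseline comorbidities". Protocol Table 3 gives the role of covariate to weight and to six baseline conditions (sleep-disordered breathing, chronic otitis media, lordosis, kyphosis, spinal stenosis, hydrocephalus), among others. SAP 7.2.1 states the selection principle as "the predictors being the variables associated with both the exposure (recifercept treatment) and the outcomes of interest", but its list is permissive: "The potential covariates may include demographics (e.g. age, gender, race and ethnicity), clinical characteristics".

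Objective 1 is met "when all of the standard mean differences for the matched variables are less than 0.1". The tested hypothesis (3.1) is "Null: Mean Change from Baseline of Height Z-Score up to 12 months is no different" between the groups. Baseline Z-score is used only descriptively in 7.2.2: "Baseline summaries of Height Z-score and Arm-Span to Height-difference". Neither the model terms listed in 7.2 nor the models coded in 10.3 include a baseline value.

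For Objective 2, 7.2.2 requires a matched dataset "exclusively with a ratio of treated to untreated of 1:1". The only matching program in 10.3 uses `varratio (kmax = 4)` and assesses balance with `weight = none`.

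**The concern.** The Objective 1 rule decides whether the external control counts as confirmed, and it opens the Objective 2 comparison. As coded, it sees three demographic variables. It cannot see the starting value of the endpoint under test, nor any clinical variable that 7.2.4 promises.

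Nothing later compensates, because the coded models regress change on month and drug alone. If children in the trial and in the natural history study start at different height Z-scores, and change depends on the starting value, part of the estimated difference would not be due to the drug.

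The matching settings add to this. The match ratio differs between 7.2.2 and 10.3, and the chance of meeting the rule depends strongly on it.

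**Working it through.** The plan gives no figure for balance or for the chance of meeting Objective 1, so there is none to reproduce.

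**1. Variables, side by side.** Table 7.2.4: demographics, clinical characteristics, comorbidities. Code in 10.3: sex, age, White. Baseline height Z-score is in neither, so adding the 7.2.4 variables would not by itself bring it under the rule.

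**2. What the rule can detect.** In a 1:1 match exact on sex and White, the standardized mean differences (SMDs) of both are 0 by construction, so the rule in effect tests age alone. In an unweighted variable-ratio set they are not forced to 0.

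**3. Bias from a baseline gap.** With no drug effect, bias in mean change = slope of change on baseline Z × gap. The documents give neither input. On assumed values (size of bias, in Z):

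| Slope | Gap 0.2 | Gap 0.5 |
|---|---|---|
| 0 | 0 | 0 |
| -0.05 | 0.01 | 0.025 |
| -0.1 | 0.02 | 0.05 |
| -0.2 | 0.04 | 0.10 |

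Assume also 63 pairs, Z with SD 1 at both times, and SD of change = √(2 × |slope|). The standard error is then SD × √(2/63). At slopes of -0.05 to -0.2, two-sided type I error at nominal 5% is 5.4-6.5% for a 0.2 gap and 7.3-14.4% for a 0.5 gap.

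**4. How often the rule passes.** Simulation on assumed inputs: 60 treated; 100, 150 or 200 eligible controls; 50% of each sex; White 75% against 65%; age shifted 0.2 SD; true baseline Z gap 0.5 SD, with Z unrelated to the three coded variables; optimal matching; 1,000 runs per cell. The ceiling on controls is 300 - 63 = 237, because trial children come from C4181001 (SAP 2) and no patient is in both datasets (SAP 2.1). Ranges run over the three control numbers.

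| Match | Coded score: pass | Median Z gap kept in passing sets (SD) | Z in score and under rule: pass | Mean Z gap left with Z in score (SD) |
|---|---|---|---|---|
| 1:1, exact sex + White, caliper 0.25 SD of logit | 96-100% | 0.50-0.51 | 68-70% | 0.01-0.02 |
| 1:1, exact sex, caliper 0.25 SD of logit | 78-80% | 0.50-0.51 | 49-56% | 0.01-0.02 |
| 1:1, exact sex, caliper 0.01 SD of logit | 49-61% | 0.50-0.53 | 6-11% | below 0.01 |
| 1:1, exact sex, caliper 0.01 on score scale | 78-79% | 0.50-0.51 | 32-43% | below 0.01 |
| Ratio up to 4, exact sex + White, unweighted, as many controls as possible | 9-15% | 0.48-0.50 | 2-3% | 0.17-0.21 |
| Same, only close extra controls | 33-54% | 0.50-0.52 | 14-49% | 0.05-0.11 |

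The last two rows are the coded kind of match. Weighting controls within set brings their residual to about 0.02 SD or less. Because Z was assumed unrelated to the coded variables, keeping the whole gap follows by construction. With an assumed Z-age correlation of 0.3, the two caliper-0.25 1:1 matches still keep 0.40-0.45 SD.

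Weighting by inverse probability (IPW, 2,000 runs) leaves 0.49-0.50 SD with the coded score and below 0.01 SD with Z added.

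**5. Noise in a reported SMD.** For a variable left out of the match, SE ≈ √(2/pairs): 0.178 at 63 pairs, 0.258 at 30. With no true gap, the chance that |SMD| exceeds 0.1 is 0.58 and 0.70. A point value alone is weak evidence of a real gap.

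**The case against.** The strongest reply is that the harm is hypothetical. The gap and the slope are assumed, and the endpoint is within-child change, so the bias is 0 unless change depends on starting height. At a 0.2 gap it is at most 0.04 Z on the slopes tried. Both cohorts come from C4181001 and share limits on weight, obesity, Tanner stage and growth-affecting treatment. This stands as a limit on size, although none of those criteria bounds height Z-score.

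Second, the match actually coded fails the rule in about half of runs or more, so it would be wrong to infer that Objective 1 is met almost automatically. That stands too: 96-100% belongs to a 1:1 match exact on sex and White, which meets 7.2.2 but is not what 10.3 codes.

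Third, 7.2.1 only says what the covariates may be, so the code does not break it; the firm conflict is with 7.2.4. A reader might also see contradictions in the exact-match variables and the caliper. The text supports less than that. The paragraph that names gender also creates the White indicator, and the caliper range is listed among options. The code states no caliper, which does not show one outside that range.

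Fourth, post-matching tables, t-tests and possibly a negative control outcome are planned, and this is a feasibility pilot for a product that protocol section 5 records as discontinued. The tables could reveal a gap, but they do not enter the Objective 1 decision.

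**Conclusion.** The point holds as a gap in the decision rule and a mismatch between code and text. The code omits the clinical covariates of 7.2.4, the rule cannot see baseline height Z-score, and `varratio (kmax = 4)` conflicts with the exclusive 1:1 ratio of 7.2.2. For IPW the gate is softer still, since 7.2.1 only allows that an SMD under 10% may be treated as negligible.

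A reader might infer that the groups do differ at baseline, or that the Objective 2 result is biased. The documents show neither: they give no baseline Z-scores and no slope. On the assumed slopes the possible bias is 0.01-0.04 Z for a 0.2 gap and 0.025-0.10 Z for a 0.5 gap, and 0 with no dependence on starting height. The text mismatch is certain; its consequence is conditional. It should be fixed, because the study exists to judge whether C4181001 can serve as a control.

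**What to change.** 1. Add baseline height Z-score to PSMODEL and ASSESS in both programs, and report its SMD with a confidence interval beside the Objective 1 decision. As a matched variable it falls under the existing 0.1 rule. The SAP should say so, and say that Objective 1 becomes harder to meet.
2. Make the code follow 7.2.2 (1:1). If a variable ratio is kept, change 7.2.2 and weight controls within set in both ASSESS and the outcome model; unweighted, adding Z still leaves 0.05-0.21 SD.
3. Align the covariate list in 10.3 with 7.2.4, and state one set of exact-match variables and one caliper with its scale. Report, without gating, SMDs for baseline arm-span-to-height difference, weight and the Table 3 baseline conditions recorded in both studies.
4. Optionally, as a sensitivity analysis only, fit a model with the baseline value as a fixed effect, noting that it can differ from the change-score model in non-randomised groups.

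Cost: wording and code, since baseline Z-score is already to be summarised. In the 1:1 match exact on sex and White, the pass rate falls from 96-100% to about 68-71%, with or without a true gap. Most of that comes from adding Z to the score: at the 0.5 SD gap, 69-71% pass even if Z is not gated. In the coded variable-ratio match left unweighted, it falls from 9-15% to 2-3% (as many controls as possible) or from 33-54% to 14-49% (close extras only). In the 1:1 matches, about 2-12 more treated children go unmatched.

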- A recifercept phase 2 clinical study (Study C4181005) is ongoing to investigate the safety, tolerability, pharmacokinetics (PK) and efficacy of recifercept in children aged 3 months to 10 years with achondroplasia. Fifty-four eligible participants aged 2-10 years and 9 patients aged 3 months to 2 years will be enrolled and randomized to receive one of three doses of recifercept subcutaneously (Img/kg once-weekly, 2mg/kg twice weekly, or 1.5mg/kg once-daily, n=21 per dose). Once participants complete the phase 2 trial, they will be offered enrollment into an open-label extension study at the dose previously received in the phase 2 trial or at the therapeutic dose once it is identified. A separate multi-country prospective observational natural history study (Study C4181001) is ongoing to examine the anthropometric characteristics, and achondroplasia. A total of 300 achondroplasia patients aged 0 and 15 years of age will be recruited and followed up for a duration of 5 years. All patients participating in Study C4181005 were or will be recruited from Study C4181001.

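### On the IPW route, a linear age term and a balance rule on means alone can let unequal shares of children under 2 years pass, which can bias the comparison of Z-score change

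*SAP*

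**What the plan says.** **Score.** Both PROC PSMATCH calls in SAP 10.3 use "psmodel DRUG (treated = 'Recifercept') = SEX AAGE WHITE". The CLASS statement is "class SEX DRUG WHITE", so AAGE is a single straight line on the logit scale, with no band, square or spline. The IPW weights come from this score (SAP 7.2.1): "Weights are calculated for each subject as 1/PS for Recifercept and 1/(1-PS) for the untreated group".

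**Balance rule.** SAP 7.2.1 states "Standardized mean differences of the matched variables are the main criteria used to determine whether objective 1 is met" and treats the external control as confirmed "when all of the standard mean differences for the matched variables are less than 0.1". For the weighted data the wording is softer: "Standardized mean differences of <10% may be considered a negligible difference". No limit is set on a variance ratio, a quantile or an age band. Review of the score distribution, trimming, boxplots and a possible negative control outcome are mentioned, but none carries a threshold for balance.

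**Age structure.** SAP 2 says "Fifty-four eligible participants aged 2-10 years and 9 patients aged 3 months to 2 years will be enrolled". Entry conditions in SAP 4.1 change at age 2: a brain/cervical spine MRI on record below it, independent standing from it. Controls may be 3 months to under 11 years old; their share under 2 is not given.

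**Use.** SAP 7.2.2 allows either the 1:1 matched or the IPW dataset for Objective 2. SAP 4.4 rules out subgroup analyses.

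**The concern.** An SMD for age compares two means, and groups with the same mean age can hold very different shares of infants. A score that is linear in age can pull the means together without equalising those shares. The trial fills two age cohorts by plan, so the odds of being a trial patient may step at age 2, which a straight line cannot follow.

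If untreated infants change differently in height Z-score, or in arm-span-to-height difference, from older children, an unequal infant share shows up as a recifercept effect, in either direction. Objective 1 would still be declared met, and with no analysis by age band nothing later in the plan would reveal it. For a feasibility study whose product is the external control itself, this is the check that matters.

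**Working it through.** The documents state no figure for age balance, so there is none to reproduce. The planned counts agree: 54 + 9 = 63 = 3 × 21, and 9/63 = 14.3%.

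**Inputs**
- From the SAP: the score model, the weights, the 0.1 limit, 63 treated with 9 under 2, and 300 planned in the natural history study (at most 300 − 63 = 237 controls if the trial patients come from it and are excluded).
- Assumed: 200 eligible controls (100 also tried); control infant share 3% to 45%; ages uniform within 0.25-2 and 2-11 years; SD of 12-month Z-score change 0.45.

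**Step 1. What a linear term misses.** Take 30% infants among controls and the same older ages in both groups. The odds of being a trial patient, infants relative to older children, are (0.143/0.30)/(0.857/0.70) = 0.476/1.224 = 0.39. On the logit scale that is a drop of 0.94 below age 2 and no slope above it. A straight line only approximates this.

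It does nothing at all when mean ages are equal. The treated mean is (9 × 1.125 + 54 × 6.5)/63 = 5.73 years. A control pool with 30% infants has the same mean if its older children average (5.73 − 0.30 × 1.125)/0.70 = 7.7 years. The age coefficient is then near zero and the infant shares stay as they were.

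**Step 2. Simulated IPW as coded** (63 treated, 200 controls, same older ages). Type I error is for a nominal 5% test with a 0.5 Z infant/older difference.

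| Control share under 2 | Weighted share, treated vs control | Infant SMD | Age, sex, White all < 0.1 | Type I error |
|---|---|---|---|---|
| 5% | 12% vs 5% | 0.21 | 99.8% of runs | at most 6.9% |
| about 15% | no mean gap | about 0 | – | about nominal |
| 30% | 19% vs 28% | 0.22 | 98-100% | 8-11% |
| 45% | 23% vs 40-41% | 0.40 | 86-92% | 21-23% |

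Check of the 30% row: SMD = (0.28 − 0.19)/√[(0.19 × 0.81 + 0.28 × 0.72)/2] = 0.09/0.42 = 0.21, which agrees up to rounding of the shares.

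With older control ages shifted so that mean ages are equal, the gap is 15-16 points at 30% infants (about 15% vs 30%) and 11-12 points at 3% (14-15% vs 3%). All three SMDs pass in essentially every run.

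**Step 3. From gap to bias.** Bias = (treated − control infant share) × (infant − older untreated change). With infants changing by 0.5 Z less:
- 30% row: (−0.09) × (−0.5) = +0.045 Z
- 45% row: (−0.17) × (−0.5) = +0.085 Z
- 30%, equal mean age: (−0.16) × (−0.5) = +0.08 Z
- 5% row, gap about 0.06-0.07: −0.030 to −0.035 Z

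With no difference in change, the bias is 0. If the age effect is smooth rather than a step at 2, type I error is 5-7%.

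**Step 4. Linear age in the outcome model.** SAP 7.2 lists age and gender as fixed effects; SAP 5.4 says covariates are not applicable, and both coded MODEL statements omit age. Putting linear age in leaves the bias almost unchanged: 0.079 before and after in the 30% equal-mean case, and 0.046 and 0.080 in the 30% and 45% rows.

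**Step 5. The 1:1 route.** Within a sex-by-White cell the logit score depends on age alone, so the match is a match on age. At a caliper of 0.25 SD of the logit (the SAP gives 0.01 to 0.25 without units), the gap was 1-3 points at 30% infants with the same older ages, 5 at 3% infants, and 5-9 when mean ages were equal. At 0.05 it was 1-4 points; at 0.01, about 1 point or less, but with only 15-38 pairs.

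**The case against.** The strongest case against has five parts.

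- **The control share may be close to the trial's.** Ages spread evenly over the eligible range give 1.75/10.75 = 16% under 2, near the point of no mean bias, and the MRI and 7 kg conditions may remove further infants. This stands. The shares of 30% and 45% are assumptions, and without the natural history protocol one cannot say whether it had age quotas.
- **A Z-score is normally standardised for age.** This stands in part. The SAP names no reference population, and the second endpoint, arm-span-to-height difference, is not described as standardised. It is also unclear how children under 2 contribute to a Z-score of standing height.
- **The plan does look at distributions.** True, but without a threshold.
- **The rule binds matched variables, and the IPW sentence is only permissive.** Correct. That leaves IPW with a weaker check.
- **The simulated outcome steps at age 2 and the remedy is an indicator at age 2.** Fair; with a smooth effect the inflation is small.

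A reader might infer three stronger points, which the documents do not support:

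- That both routes are affected alike. Exact matching on sex and White makes the matched route an age match; what remains comes from a loose caliper or scarce infants.
- That mean age is the only thing the matched check can fail on. The code is "match method = varratio (kmax = 4) distance = lps exact = (SEX WHITE") with unweighted assessment, so sex and White can also become unbalanced. That code conflicts with the 1:1 restriction in SAP 7.2.2.
- That type I error reaches 39%. This needs 45% infant controls and a 1.0 Z difference, over twice the assumed SD.

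**Conclusion.** The point holds for IPW, conditionally. As coded, a gap of about 6 to 17 points in weighted infant share, two to four times the SAP's own SMD limit, can remain while every checked variable passes. It *can* bias the Objective 2 comparison; the documents do not show that it *does*. Two unstated facts decide this: the share under 2 among eligible controls, and whether untreated change differs by age. With a 0.5 Z step, the bias is about 0.03 to 0.085 Z in the scenarios shown. It is nil on average if the control share is near 15% or if change does not vary with age. The linear age term in SAP 7.2 is no safeguard. The 1:1 route needs the check more than it needs a new model.

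**What to change.** 1. Derive the trial's age cohort at baseline (under 2 / 2 years and over), using the baseline dates in SAP 5. Add it to CLASS and to both psmodel statements, keeping AAGE. IPW is where it matters most.
2. List it in ASSESS (the IPW call names its variables explicitly) and state in SAP 7.2.1 that it must meet the 0.1 limit in both the weighted and the matched dataset. Make the limit a requirement for IPW, not an option.
3. Exact matching on cohort is optional for the 1:1 route.
4. Report the number of eligible controls in each cohort, name the Z-score reference, and reconcile SAP 7.2, SAP 5.4 and the code on age in the outcome model.

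**Effect.** With the indicator in the IPW score, the mean infant SMD falls to 0.03 or less and type I error to about 4-5%.

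**Cost.** One derived variable and a few code lines. Weights become slightly larger, and the balance rule fails more often when overlap is poor: about 60-65% of runs pass at 45% infant controls, against 86-92% now. That is information the linear score hides. Exact cohort matching, if used, keeps 53-58 of 63 pairs with 100 controls and 58-63 with 200. In the least favourable setting tried (30% infants, equal mean age) the rule then passes in 62% and 91% of runs respectively.
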